15.5. Audit

An audit is a systematic and independent review of study related activities and documents to determine whether the validated study related activities were conducted and the data were recorded, analysed and accurately reported according to the protocol, designated Standard Operating Procedure (SOPs), Good Clinical Practice (GCP) and the applicable regulatory requirements. An independent audit at the study site may take place at any time during or after the study.

16. ETHICAL AND LEGAL CONSIDERATIONS

16.1. Ethical Considerations

Before initiating a study, the Investigator will have written and dated approval / favourable opinion from the relevant IRB / IEC for the study protocol as well as for any amendments. Approval will be indicated in writing with reference to the final protocol number and date. Details of the IRB / IEC's constitution including names of its members and their function in the committee (e.g. chairman, specialist, lay-member) should be made available for inclusion in the Trial Master File.During the study all documents that are subject to review should be provided to the IRB / IEC by the Investigator.

16.2. Independent Ethics Committee (IEC) / Institutional Review Board (IRB)

The study protocol including all amendments and the study CRF will be submitted to the IRB/EC of the study centre before initiation of the study. IRB/EC approval for the study protocol and all amendments will be obtained prior to the start of any study specific procedures.

Date: 040418

STUDY ID: CAPTAIN - rTMS

16.3. Informed Consent

Patients will be informed about the study procedures and potential risks and benefits of the study. Their consent to participate in this study will be obtained before any study-specific procedures are carried out.

16.4. Modification of Protocol

The Investigator or the Sponsor should not implement any deviation from, or changes of, the protocol without mutual agreement, prior review and documented approval from the IEC of a respective amendment. The only exceptions are where necessary to eliminate an immediate hazard to study patients, or when the changes involve only logistical or administrative aspects of the study (e.g. change in monitor(s), change of telephone number(s)).

The party initiating an amendment must confirm it clearly in writing and it must be signed and dated by the Sponsor and the Principal Investigator. Necessary protocol amendments will be submitted to the appropriate IECs.

16.5. Conduct of Study

This clinical study will be conducted in accordance with the Declaration of Helsinki. It will be conducted in compliance with this protocol, Good Clinical Practice (2001/20/ EEC, CPMP/ICH/135/95), designated Standard Operating Procedures, and with local laws and regulations relevant to the use of investigational new drugs in the country of conduct.

16.6. Personal Data and Data Protection

All data obtained in the context of the clinical study are subject to data protection. The patient's name in addition to other data related to persons (excluding date of birth / age and sex) are not to be disclosed by the Investigator or the investigating physicians. The latter shall take care that the case report forms or other documents (e.g. copies of reports on special findings) transmitted to the FSNN contain no names, but another identifier. The storage of data for statistical assessment shall be performed under the patient's identifier. Only the Investigator and the investigating physicians can perform assignment of the identifier to the personal data.

If it becomes necessary in the course of the study to identify a patient's name for medical reasons, all the individuals involved are subject to an obligation to maintain secrecy.

If personal data are stored and processed, the requirements of data protection legislation are to be observed.

16.7. Data Handling and Record Keeping

16.7.1. Completion of Case Report Forms

Any data to be recorded directly into the CRFs will be identified at the start of the study.

The investigator must ensure the accuracy, completeness legibility and timeliness of data reported in the CRF and all required reports. Any change or correction to a paper CRF must be dated, initialled and explained (in case of an eCRF data entries are already monitored by an audit trail) and must not obscure the original entry, this applies to both written and electronic changes.

Data reported on the CRF that are derived from source documents should be consistent with the source documents or the discrepancies should be explained.

Within two weeks after completion of each patient, the Investigator should agree to have completed and signed CRFs available for full inspection by the clinical monitor.

16.7.2. Archiving

On termination of the study, the study documents, including the emergency envelopes are to be returned to the Sponsor. These records are to be retained for the periods required by ICH-GCP, i. e. until at least 2 years after the last approval of a marketing application in an ICH region and until there are no pending or contemplated marketing applications in an ICH region or at least 2 years have elapsed since the formal discontinuation of clinical development of the Investigational Product (CPMP/ICH/135/95), or by national legal requirements, whichever is longer, but not less than 15 years after routine/premature termination of a clinical study.

The final report shall be retained for at least 2 years after the Investigational Products are removed from the last market. The informed consent forms and all the original (raw) data are to be retained by the head of the clinical study or the investigating physicians for at least 15 years.

16.8. Confidentiality

The aim and contents of the study, in addition to its results are to be treated as confidential by all persons involved in the clinical study.

Date: 040418

STUDY ID: CAPTAIN - rTMS

16.9. Responsibilities

The responsibilities of the Investigator, Monitor and Sponsor of the clinical study as regards handling of data, storage of data, planning, assessment and quality assurance are regulated by the recommendations on "Good Clinical Practice" of the "International Conference on Harmonisation" (ICH) and apply to this clinical study.

17. FINAL REPORT AND PUBLICATION POLICY

The Sponsor and Investigator shall agree on the final study report. The latter is to be signed by the Investigator and the investigating physicians involved.

It is intended that the results of the study may be published as scientific literature. Results may also be used in submissions to regulatory authorities. The following conditions are to protect commercial confidential materials (patents, etc.), not to restrict publication.

All information concerning the Investigational Product (such as patent applications, formulae, manufacturing processes, basic scientific data, or formulation information supplied to the Investigator by the Sponsor and not previously published) is considered confidential and shall remain the sole property of the Sponsor. The Investigator agrees not to use it for other purposes without the Sponsor's written consent.

It is understood by the Investigator that the Sponsor will use the information developed in this clinical study in connection with the development of the Investigational Product and therefore may be disclosed as required to other Investigators or any appropriate international Regulatory Authorities. In order to allow for the use of information derived from this clinical study, the Investigator understands that he/she has an obligation to provide the Sponsor with complete test results and all data developed during this study.

1. BACKGROUND

After an acute brain lesion, there is always an endogenous continuous brain defense response consisting of two main sequences: an immediate one that aims to reduce brain damage, known as neuroprotection, and a later one that aims to repair the brain damage, known as neurorecovery, which is based on neurotrophicity, neuroplasticity and neuro-genesis.

Neurotrophic factors are the most important endogenous molecules involved in brain protection and recovery. Cerebrolysin has a neurotrophic factor-like activity based on the four important endogenous neurobiological processes: neurotrophicity, neuroprotection, neuroplasticity and neurogenesis. Additionally, this activity may have similar effects as the real sequence of endogenous post-lesional regulation.

Transcranial magnetic stimulation (TMS) operates on Faraday's principle of electromagnetic induction. There are several studies regarding a beneficial role of repetitive TMS (rTMS) in neurorehabilitation, including in TBI patients such as: motor recovery including spasticity, depression treatment, and speech rehabilitation. Regarding rTMS as an add-on to pharmacological treatment in cognitive rehabilitation, there are too few data to establish its efficacy. There are several studies on rTMS as add-on treatment in depression, with good results when the magnetic stimulation was performed with high frequencies. In TBI, this study is the first one in order to test the efficacy of the combining treatment rTMS + pharmacological intervention (CRB) in cognitive rehabilitation.

2. DEFINITIONS AND ABBREVIATIONS

| AE | Adverse Event |
|--------|---|
| A(D)R | Adverse (Drug) Reaction |
| CANTAB | Cambridge Neuropsychological Test Automated Battery |
| CRB | Cerebrolysin |
| CRF | Case Report Form |
| CRO | Contract Research Organisation |
| СТ | Computed tomography |
| DLPFC | Dorso-lateral pre-frontal cortex |
| ET | Eye tracking |
| FSNN | Foundation for the Study of Neuroprotection and Neuroplasticity |
| GCP | Good Clinical Practice |
| GCS | Glasgow Coma Scale |
| GOS-E | Extended Gasgow Outcome Scale |

Version 1.0

Cerebrolysin and repetitive Transcranial Magnetic Stimulation (rTMS) in patients with Traumatic Brain Injury

| Н | Hour |
|---------|---|
| HAM-A | Hamilton Anxiety Rating Scale |
| HAM-D | Hamilton Rating Scale for Depression |
| Hz | Hertz |
| ICH | International Conference for Harmonization |
| IEC | Independent Ethics Committee |
| IMP | Investigational Medicinal Product |
| incl. | including |
| IUD | Intrauterine device |
| IV | Intra-venous |
| mL | Milli Liter |
| MoCA | Montreal Cognitive Assessment Scale |
| MRI | Magnetic resonance imaging |
| MTT | Multi-tasking test |
| NA | Not Applicable |
| OTS | One Touch Stocking of Cambridge |
| PLC | Placebo |
| PSI | Processing Speed Index |
| qEEG | Qantitative electroencephalography |
| rTMS | Repetitive transcranial magnetic stimulation |
| RT | Reaction Time |
| SAE | Serious Adverse Event |
| SAP | Statistical Analyses Plan |
| SAR | Serious Adverse Reaction |
| SESAR | Suspected Expected Serious Adverse Reaction |
| SOP | Standard Operating Procedure |
| SmPC | Summary of Product Characteristics |
| SUSAR | Suspected Unexpected Serious Adverse Reaction |
| TBI | Traumatic Brain Injury |
| WAIS | Wechsler Adult Intelligence Scale |
| WHO-UMC | World Health Organization-Uppsala Monitoring Center |

3. SOFTWARE UTILIZED

Statistical procedures were performed using the R programming language and SAS® OnDemand for Academics.

4. CODING SYSTEMS UTILIZED

All variables were coded to create the primary efficacy analysis.

| AGE | Age of patients |
|-------|----------------------------|
| COMP1 | Composite score at Day 100 |

Cerebrolysin and repetitive Transcranial Magnetic Stimulation (rTMS) in patients with Traumatic Brain Injury

Version 1.0

| COMP2 | Composite score at Day 180 |
|-------------------|--|
| CWTTM1_1 | Stroop Color Word Test – Word Task - Number of seconds at Visit 1 - Baseline |
| CWTTM1_2 | Stroop Color Word Test – Word Task - Number of seconds at Visit 2 – Day 100 |
| CWTTM1_3 | Stroop Color Word Test – Word Task - Number of seconds at Visit 3 – Day 180 |
| CWTTM2_1 | Stroop Color Word Test – ColorTask - Number of seconds at Visit 1 - Baseline |
| CWTTM2_2 | Stroop Color Word Test – Color Task - Number of seconds at Visit 2 – Day 100 |
| CWTTM2_3 | Stroop Color Word Test – Color Task - Number of seconds at Visit 3 – Day 180 |
| CWTTM3_1 | Stroop Color Word Test – Color-Word Task - Number of seconds at Visit 1 - Baseline |
| CWTTM3_2 | Stroop Color Word Test – Color-Word Task - Number of seconds at Visit 2 – Day 100 |
| CWTTM3_3 | Stroop Color Word Test – Color-Word Task - Number of seconds at Visit 3 – Day 180 |
| DGBRES_1 | Digit Span – Digit Backward Total Score at Visit 1 - Baseline |
| DGBRES_2 | Digit Span – Digit Backward Total Score at Visit 2 – Day 100 |
| DGBRES_3 | Digit Span – Digit Backward Total Score at Visit 3 – Day 180 |
| DGFRES_1 | Digit Span – Digit Forward Total Score at Visit 1 - Baseline |
| DGFRES_2 | Digit Span – Digit Forward Total Score at Visit 2 – Day 100 |
| DGFRES_3 | Digit Span – Digit Forward Total Score at Visit 3 – Day 180 |
| DS_B_v1-baseline | Digit Span Backward Baseline Difference Day 100 |
| DS_B_v2-baseline | Digit Span Backward Baseline Difference Day 180 |
| DS_F_v1-baseline | Digit Span Forward Baseline Difference Day 100 |
| DS_F_v2-baseline | Digit Span Forward Baseline Difference Day 180 |
| D_PRESDT_VISDTC_2 | D_PRESDT_VISDTC_2 |
| D_PRESDT_VISDTC_3 | D_PRESDT_VISDTC_3 |
| GROUP | GROUP |
| HADS_v1-baseline | Hamilton Anxiety Rating Scale Baseline Difference Day 100 |
| HADS_v2-baseline | Hamilton Anxiety Rating Scale Baseline Difference Day 180 |
| HARTS_1 | Hamilton Anxiety Rating Scale - Total score at Visit 1 - Baseline |
| HARTS_2 | Hamilton Anxiety Rating Scale - Total score at Visit 2 – Day 100 |
| HARTS_3 | Hamilton Anxiety Rating Scale - Total score at Visit 3 – Day 180 |
| HDRS_v1-baseline | Hamilton Depression Rating Scale Baseline Difference Day 100 |
| HDRS_v2-baseline | Hamilton Depression Rating Scale Baseline Difference Day 180 |
| HDTS_1 | Hamilton Depression Rating Scale - Total score at Visit 1 - Baseline |
| HDTS_2 | Hamilton Depression Rating Scale - Total score at Visit 2 – Day 100 |
| HDTS_3 | Hamilton Depression Rating Scale - Total score at Visit 3 – Day 180 |
| MOCA_v1-baseline | Montreal Cognitive Assessment Baseline Difference Day 100 |
| MOCA_v2-baseline | Montreal Cognitive Assessment Baseline Difference Day 180 |
| MOTS_1 | Montreal Cognitive Assessment – Total Score at Visit 1 - Baseline |
| MOTS_2 | Montreal Cognitive Assessment – Total Score at Visit 2 – Day 100 |
| MOTS_3 | Montreal Cognitive Assessment – Total Score at Visit 3 – Day 180 |
| MTT1_v1-baseline | CANTAB Multitasking Test – Total Correct Baseline Difference Day 100 |
| MTT1_v2-baseline | CANTAB Multitasking Test – Total Correct Baseline Difference Day 180 |
| MTT2_v1-baseline | CANTAB Multitasking Test – Total Incorrect Baseline Difference Day 100 |
| MTT2_v2-baseline | CANTAB Multitasking Test – Total Incorrect Baseline Difference Day 180 |
| MTTTC01_1 | CANTAB Multitasking Test – Total Correct at Visit 1 - Baseline |
| MTTTC01_2 | CANTAB Multitasking Test – Total Correct at Visit 2 – Day 100 |
| MTTTC01_3 | CANTAB Multitasking Test – Total Correct at Visit 3 – Day 180 |

Cerebrolysin and repetitive Transcranial Magnetic Stimulation (rTMS) in patients with Traumatic Brain Injury

Version 1.0

| MTTTC02_1 | CANTAB Multitasking Test – Total Incorrect at Visit 1 - Baseline |
|---------------------|--|
| MTTTC02_2 | CANTAB Multitasking Test – Total Incorrect at Visit 2 – Day 100 |
| MTTTC02_3 | CANTAB Multitasking Test – Total Inorrect at Visit 3 – Day 180 |
| OTS01_1 | CANTAB One Touch Stockings of Cambridge-Problems solved on first choice at Visit 1 - Baseline |
| OTS01_2 | CANTAB One Touch Stockings of Cambridge-Problems solved on first choice at Visit 2 – Day 100 |
| OTS01_3 | CANTAB One Touch Stockings of Cambridge-Problems solved on first choice at Visit 3 – Day 180 |
| OTS02_1 | CANTAB One Touch Stokings of Cambridge-Mean choices to correct at Visit 1 - Baseline |
| OTS02_2 | CANTAB One Touch Stokings of Cambridge-Mean choices to correct at Visit 2 – Day 100 |
| OTS02_3 | CANTAB One Touch Stokings of Cambridge-Mean choices to correct at Visit 3 – Day 180 |
| OTS1_v1-baseline | CANTAB One Touch Stockings of Cambridge-Problems solved on first choice Baseline Difference Day 100 |
| OTS1_v2-baseline | CANTAB One Touch Stockings of Cambridge-Problems solved on first choice Baseline Difference Day 180 |
| OTS2_v1-baseline | CANTAB One Touch Stokings of Cambridge-Mean choices to correct Baseline Difference Day 100 |
| OTS2_v2-baseline | CANTAB One Touch Stokings of Cambridge-Mean choices to correct Baseline Difference Day 180 |
| PRESDT | Presentation Date |
| PSCNUM_1 | Processing Speed Index – Digit Symbol Coding Number Correct at Visit 1- Baseline |
| PSCNUM_2 | Processing Speed Index – Digit Symbol Coding Number Correct at Visit 2 – Day 100 |
| PSCNUM_3 | Processing Speed Index – Digit Symbol Coding Number Correct at Visit 3 – Day 180 |
| PSI_DSC_v1-baseline | Processing Speed Index – Digit Symbol Coding Number Correct Baseline Difference Day 100 |
| PSI_DSC_v2-baseline | Processing Speed Index – Digit Symbol Coding Number Correct Baseline Difference Day 180 |
| PSI_SS_v1-baseline | Processing Speed Index – Symbol Search Number Correct Baseline Difference Day 100 |
| PSI_SS_v2-baseline | Processing Speed Index – Symbol Search Number Correct Baseline Difference Day 180 |
| PSSCNUM_1 | Processing Speed Index – Symbol Search Number Correct at Visit 1 - Baseline |
| PSSCNUM_2 | Processing Speed Index – Symbol Search Number Correct at Visit 2 – Day 100 |
| PSSCNUM_3 | Processing Speed Index – Symbol Search Number Correct at Visit 3 – Day 180 |
| PSSINUM_1 | Processing Speed Index – Symbol Search Number Incorrect at Visit 1 - Baseline |
| PSSINUM_2 | Processing Speed Index – Symbol Search Number Incorrect at Visit 2 – Day 100 |
| PSSINUM_3 | Processing Speed Index – Symbol Search Number Incorrect at Visit 3 – Day 180 |
| RTI1_v1-baseline | CANTAB RTI - Five choice movement time - Raw score Baseline Difference Day 100 |
| RTI1_v2-baseline | CANTAB RTI - Five choice movement time - Raw score Baseline Difference Day 180 |
| RTI2_v1-baseline | CANTAB RTI - Mean reaction time - Raw score Baseline Difference Day 100 |
| RTI2_v2-baseline | CANTAB RTI - Mean reaction time - Raw score Baseline Difference Day 180 |
| RTIFMRT_1 | CANTAB RTI - Five choice movement time - Raw score at Visit 1 - Baseline |
| RTIFMRT_2 | CANTAB RTI - Five choice movement time - Raw score at Visit 2 – Day 100 |
| RTIFMRT_3 | CANTAB RTI - Five choice movement time - Raw score at Visit 3 – Day 180 |
| RTISMRT_1 | CANTAB RTI - Mean reaction time - Raw score at Visit 1 - Baseline |
| RTISMRT_2 | CANTAB RTI - Mean reaction time - Raw score at Visit 2 – Day 100 |

Cerebrolysin and repetitive Transcranial Magnetic Stimulation (rTMS) in patients with Traumatic Brain Injury

Version 1.0

| RTISMRT_3 | CANTAB RTI - Mean reaction time - Raw score at Visit 3 – Day 180 |
|------------------------|---|
| SCWT_C-D_1 | SCWT_C-D_1 |
| SCWT_C-D_2 | SCWT_C-D_2 |
| SCWT_C-D_2_1 | SCWT_C-D_2_1 |
| SCWT_C-D_v1-baseline | SCWT_C-D_v1-baseline |
| SCWT_C-D_v2-baseline | SCWT_C-D_v2-baseline |
| SCWT_W-D_1 | SCWT_W-D_1 |
| SCWT_W-D_2 | SCWT_W-D_2 |
| SCWT_W-D_2_1 | SCWT_W-D_2_1 |
| SCWT_W-D_v1-baseline | SCWT_W-D_v1-baseline |
| SCWT_W-D_v2-baseline | SCWT_W-D_v2-baseline |
| SEX | Sex of patient |
| SUBJECT | Number of subject |
| TMRES01_1 | Trial Making Test 1 - Time in seconds at Visit 1 - Baseline |
| TMRES01_2 | Trial Making Test 1 - Time in seconds at Visit 2 – Day 100 |
| TMRES01_3 | Trial Making Test 1 - Time in seconds at Visit 3 – Day 180 |
| TMRES05_1 | Trial Making Test 2 - Time in seconds at Visit 1 - Baseline |
| TMRES05_2 | Trial Making Test 2 - Time in seconds at Visit 2 – Day 100 |
| TMRES05_3 | Trial Making Test 2 - Time in seconds at Visit 3 – Day 180 |
| TMT1_1_truncated | Trial Making Test 1 - Time in seconds at Visit 1 – Baseline - truncated |
| TMT1_2_truncated | Trial Making Test 1 - Time in seconds at Visit 2 – Day 100 - truncated |
| TMT1_3_truncated | Trial Making Test 1 - Time in seconds at Visit 3 – Day 180 - truncated |
| TMT1_v1-baseline | Trial Making Test 1 - Time in seconds Baseline Difference Day 100 |
| TMT1_v2-baseline | Trial Making Test 1 - Time in seconds Baseline Difference Day 180 |
| TMT2_1_truncated | Trial Making Test 2 - Time in seconds at Visit 1 – Baseline - truncated |
| TMT2_2_truncated | Trial Making Test 2 - Time in seconds at Visit 2 – Day 100- truncated |
| TMT2_3_truncated | Trial Making Test 2 - Time in seconds at Visit 3 – Day 180 - truncated |
| TMT2_v1-baseline | Trial Making Test 2 - Time in seconds Baseline Difference Day 100 |
| TMT2_v2-baseline | Trial Making Test 2 - Time in seconds Baseline Difference Day 180 |
| VISDTC_1 | Visit 1 (Baseline Visit) - Date |
| VISDTC_2 | Visit 2 Day 100 - Date |
| VISDTC_2_PROTOCOL_DIFF | VISDTC_2_PROTOCOL_DIFF |
| VISDTC_3 | Visit 3 Day 180 - Date |
| VISDTC_3_PROTOCOL_DIFF | VISDTC_3_PROTOCOL_DIFF |

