13.7. Level of Significance

The multiple level alpha is set to α = 0.05, one-sided, according to current recommendations for randomized phase II trials (Rubinstein 2009; Sumithra 2010; Manish 2011).

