13.9. Sample Size Calculation

The power for this study is determined based on the following design specifications:

- (a) One-sided type I error defined as alpha = 0.05 (multiple level alpha, see section 13.7)
- (b) Type II error defined as $\beta = 0.2$ (Testpower 80%)
- (c) Design alternative effect size: Mann-Whitney statistic (MW) = 0.64 (medium-sized difference according to Cohen (Colditz, 1988); assuming a normal distribution the effect size MW may easily be re-expressed as the well-known Cohen effect size (Cohen, 1988) of a standardized difference (Cohen's d): MW = 0.64 means Cohen's d = 0.5)
- (d) Estimated correlations among the single outcome scales included in the global statistics $\rho = 0.4$)

Nonparametric sample size calculations within the framework of a multiple outcome approach (Wei-Lachin procedure- Wei and Lachin, 1984; Lachin 1992) was performed applying the validated software Nnpar 1.0 from idv Data Analysis and Study Planning, Krailling/Munich (see also Tang, 1989; Lachin, 1981). A good example for sample size calculation according to the Lachin approach (Wei and Lachin, 1984; Lachin 1992; Lachin, 1981) in multidimensional trials with neuroprotective agents is also given by Huang (2008).

Please note: further details of the effect size (Mann-Whitney statistic) are described in section 13.10, further details of sample size assessment are described in the separate document "Sample Size Assessment Based on a Multidimensional Efficacy Approach".

Based on the above design specifications, the total required sample size for the multivariate ensemble results in 30 patients per group (including 10% enhancement for usual "ambiguities", e.g., dropouts). With this sample size a "medium-sized" group difference (MW = 0.64) with regard to the multivariate outcome ensemble at month 3 and 6 can be detected with a power of 80%.

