8.2.1. Efficacy

An ensemble of appropriate single efficacy criteria shall be tested by a multivariate, directional test approach, reflecting the "global status of patients in TBI" (Bagiella, 2010), while simultaneously combining two points in time in the sense of a 'repeated measures design'.

The following ensemble of appropriate single efficacy criteria shall be tested by a multivariate, directional test approach, reflecting the global status of patients in TBI after 3 and 6 months:

Multivariate Efficacy Ensemble

- 1. Processing Speed Index, Changes from Baseline, LPCF, ITT
- 2. Stroop Color-Word Test, Changes from Baseline, LPCF, ITT
- 3. Trail Making Test, Changes from Baseline, LPCF, ITT

Cerebrolysin and repetitive Transcranial Magnetic Stimulation (rTMS) in patients with Traumatic Brain Injury

Version 1.0

- 4. Digit Span, Changes from Baseline, LPCF, ITT
- 5. Montreal Cognitive Assessment, Changes from Baseline, LPCF, ITT
- 6. Stockings of Cambridge (CANTAB), Changes from Baseline, LPCF, ITT
- 7. Reaction Time (CANTAB), Changes from Baseline, LPCF, ITT
- 8 Hamilton Rating Scale for Depression, Changes from Baseline, LPCF, ITT
- 9. Hamilton Anxiety Rating Scale, Changes from Baseline, LPCF, ITT

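### SAP 4 lists two undefined per-visit composites for the primary analysis, unranked against the two-visit ensemble that the protocol makes primary

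*SAP*

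**What the plan says.** **Protocol.** Sections 13.4.1 and 13.4.2 define one primary quantity, a nine-scale ensemble tested directionally with months 3 and 6 taken together. Section 13.10 names the test: a directional Wei-Lachin procedure, which averages univariate Mann-Whitney results. Section 13.7 sets the level: "The multiple level alpha is set to α = 0.05, one-sided". Section 13.8 places the control of multiplicity over outcomes and over the two visits inside that single test. Section 13.9 sizes the trial for the same ensemble, at 30 per group.

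**SAP, endpoint sections.** SAP 8.2.1 repeats the ensemble, to be tested "while simultaneously combining two points in time in the sense of a 'repeated measures design". SAP 9 lists the same nine scales for the same directional test after 3 and 6 months.

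**SAP, variable list.** SAP 4 opens with "All variables were coded to create the primary efficacy analysis" and lists COMP1 ("Composite score at Day 100") and COMP2 ("Composite score at Day 180"). The composites appear nowhere else in either document.

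**SAP, confirmatory section.** The second of the two sections numbered 12.2 promises pre-specified primary analyses and control of the multiple alpha level. The only method it gives is Kruskal-Wallis followed by Dunn's test, with Bonferroni stated for the pairwise group comparisons. It states no alpha value, no sidedness and no rule for the two visits. Wei-Lachin is not mentioned in the SAP.

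**The concern.** A per-visit composite is a different endpoint from the two-visit ensemble on which the sample size rests. Wei-Lachin does not need a score per patient, because it combines scale-level Mann-Whitney statistics. Kruskal-Wallis does need one, and COMP1 and COMP2 are the only listed variables labelled as combining scales. Someone following SAP 4 together with the confirmatory section could therefore produce two per-visit verdicts and no ensemble test.

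The composites cannot be reconstructed either. SAP 8.1 lists ten scales and SAP 9 lists nine, several scales have two or more coded variables, and no scaling or direction is given.

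Two things are at stake. The ensemble, COMP1 and COMP2 can disagree on the same data, and no rule says which one counts. In addition, a claim resting on one composite falls outside the multiplicity control in protocol 13.8, which works only inside the single two-visit test.

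**Working it through.** **Inputs from the documents.** One-sided alpha 0.05 and power 80% (protocol 13.7, 13.9); effect size "Mann-Whitney statistic (MW) = 0.64"; "Estimated correlations among the single outcome scales included in the global statistics" of 0.4; 30 per group including 10% (protocol 13.9).

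**Assumed.** The correlation r between the two composites, and any rule for claiming success on them. The documents give neither.

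**1. The plan's own figure.** For a single Wilcoxon test, n per arm = (1.645 + 0.842)² / (6 × 0.14²) = 52.6. Averaging K scales correlated at 0.4 multiplies this by (1 + (K − 1) × 0.4)/K.
- K = 9: factor 0.467, n = 24.5, rounded up to 25; 25/0.9 gives 28.
- K = 18 (nine scales at two visits): factor 0.433, n = 22.8, rounded up to 23; 23/0.9 gives 26.

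The stated 30 is close to the K = 9 result. The number of components used is not stated, and the error rates below do not depend on it.

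**2. Correlation implied by the protocol's 0.4.** Suppose 0.4 held between all 18 scale-by-visit components. Two nine-scale averages would then correlate at 9 × 0.4/(1 + 8 × 0.4) = 3.6/4.2 = 0.857. The 0.4 is a between-scale figure and should not itself be used as r.

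**3. Either composite at unadjusted one-sided 0.05.** Error rate = 1 − P(Z₁ ≤ 1.645, Z₂ ≤ 1.645), with Z₁, Z₂ bivariate normal with correlation r.

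| r | either composite | plus ensemble as a third route |
|---|---|---|
| 0 | 0.098 | 0.110 |
| 0.3 | 0.093 | 0.100 |
| 0.5 | 0.088 | 0.092 |
| 0.7 | 0.080 | 0.082 |
| 0.857 | 0.072 | 0.072 |
| 0.95 | 0.063 | 0.063 |

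**4. The SAP's own tests on the composites (30 per arm).**
- Kruskal-Wallis omnibus at two-sided 0.05 (assumed), significant at either visit: about 7–9% by simulation (0.075 at r = 0.857, 0.094 at r = 0.4).
- Dunn with Bonferroni over three pairs at two-sided 0.05 (assumed): the favourable tail is 0.05/6 = 0.0083 per visit, critical value 2.394. A false favourable result for CRB + rTMS versus CRB + sham on either composite has probability 0.013 (r = 0.857) to 0.016 (r = 0.3).
- Adding the ensemble at one-sided 0.05 to that Dunn route: about 5.0–5.6%.

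**5. How often the visits would disagree.** Assume equal effects at both visits, scaled so that the two-visit average has 80% power. Each visit's statistic then has mean (1.645 + 0.842) × √((1 + r)/2), and P(exactly one significant) = 2 × (single-visit power − P(both)).
- r = 0.3: 2 × (0.640 − 0.454) = 0.37
- r = 0.5: 2 × (0.694 − 0.550) = 0.29
- r = 0.857: 2 × (0.774 − 0.709) = 0.13

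**The case against.** The strongest reply is that the SAP 4 sentence introduces the whole data dictionary, including age, sex, subject number and visit dates. It gives COMP1 and COMP2 no more primary standing than age. No endpoint section names a composite, and no section says that success at either visit is enough. This stands as far as it goes: the composites are two labels, not a declared primary analysis. It does not close the gap, because a composite outcome listed for the primary efficacy analysis and then left undefined is a candidate endpoint in a way that age is not.

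Second, the SAP's stated pairwise method is conservative. If Dunn-Bonferroni over three pairs at two-sided 0.05 applied to the composites, inflation for the primary comparison would be negligible (step 4). This also stands. However, the SAP gives neither the level nor the sidedness, and it does not say which test the composites receive.

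Third, disagreement between visits under a true effect reflects lower single-visit power and is not a false positive. That is correct. It bears on which verdict counts, not on type I error.

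Finally, both documents call the study exploratory in nature. They also commit to confirmatory principles and control of the multiple level, so naming one primary result remains their own standard.

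**Conclusion.** The inconsistency holds. One two-visit ensemble is primary in the protocol and in SAP 8.2.1 and 9. SAP 4 adds two undefined per-visit composites. The SAP's confirmatory section contains no test of the ensemble and no rule across visits.

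A reader might infer that the trial has a false-positive rate near 9%. The documents do not support that as a property of the plan. It requires each composite to be tested at unadjusted one-sided 0.05, success to be claimed on either, and a correlation of about 0.5 or lower between composites. None of these is stated. Under the first two conditions the rate is about 6–10% over correlations from 0.95 to 0, and about 7% at the 0.857 implied if 0.4 held for all components. A Kruskal-Wallis omnibus at either visit gives about 7–9%. Dunn-Bonferroni gives about 1.3–1.6% for the primary comparison.

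The ambiguity about which result decides does not depend on those rates. At 80% ensemble power with equal effects, about 13% (r = 0.857) to 37% (r = 0.3) of trials would have exactly one significant visit. The SAP should be corrected before unblinding.

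**What to change.** Change three places in the SAP.

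- **SAP 9 and the confirmatory section (12.2):** state that the sole primary result is the two-visit ensemble comparison of CRB + rTMS with CRB + sham rTMS, tested by the protocol's directional Wei-Lachin procedure at one-sided 0.05. Naming the test matters: demoting the composites alone would leave the SAP with no test of the ensemble.
- **SAP 4:** either delete COMP1 and COMP2, or give their components, scaling and direction and label them exploratory.
- **Confirmatory section (12.2):** if the composites stay, state that they and their Kruskal-Wallis/Dunn tests are exploratory and support no efficacy claim.

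With one named primary test, the error rate for the primary claim is the declared 5%. The cost is SAP wording plus programming of the Wei-Lachin test that the protocol already requires. No data, visits or patients are added, and the composites can still be reported.
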